10.2.2.4 Efficacy Analyses

10.2.2.4.1 Primary Efficacy Analysis

The primary efficacy analysis will be the evaluation of OS and PFS based on the ITT Population.

Overall survival is defined as the time interval from randomization to death of any cause. Patients who are alive will be censored at the last known date alive or data analysis cutoff date, whichever is earlier. PFS is defined as the time interval from randomization to tumor progression or death. Accordingly, the precise definition of progression and the timing of imaging scans to progression are very important. Every effort must be made to assure that timeframes for follow-up imaging scans are achieved, so that both treatment groups can be usefully compared. Assessments must be adequate to evaluate target lesions, non-target lesions, and to search for new lesions.

PFS will be based on RECIST 1.1 response guidelines modified to use irRC-specific confirmation. PFS will be defined as the time from randomization to disease progression or death (any cause), whichever occurs first. The irRC modification requires a confirmation of progressive disease (PD) at least 4 weeks later with imaging; once confirmed, the date of progression is defined as the first date that the total tumor burden was shown to have increased by at least 20% compared with the nadir. Patients who do not have disease progression or have not died will be censored at the date when the last tumor assessment determines a lack of progression. If a patient begins a new anti-cancer therapy or has radiotherapy or surgery at a lesion site prior to confirmed progression (or death), the patient will be censored at the last assessment where the patient was documented as progression free prior to the intervention. Patients with two or more missing response assessments prior to a visit with progression (or death) will be censored at the last visit where the patient is documented to be progression free.

The primary efficacy analysis will be the evaluation of OS and PFS using Kaplan-Meier methodology and will be performed on the ITT Population for each treatment arm. Kaplan-Meier plots and 95% confidence intervals (CIs) for 75%, 50% and 25% survival, if reached, will be provided for each treatment group.

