# **5 STUDY ENDPOINTS**

# 5.1 Efficacy Endpoints

# 5.1.1 Primary Efficacy Endpoint

# 5.1.1.1 **Progression free Survival (PFS)**

PFS will be based on RECIST 1.1 response guidelines modified to use irRC-specific confirmation. Progression-free survival (PFS) in months is calculated as: (date of first progression or death (any reason) – date of randomization +1)/30.4375. The irRC modification requires a confirmation of progressive disease (PD) at least 4 weeks later with imaging; once confirmed, the date of progression is defined as the first date the total tumor burden was shown to have increased by at least 20% compared with nadir. Patients without progression or death are censored at the date of the last disease assessment. If a patient begins a new anti-cancer therapy or has radiotherapy or surgery at a lesion site prior to confirmed progression (or death), the patient will be censored at the last assessment where the patient was documented as progression free prior to the intervention. Patients with two or more missing response assessments prior to a visit with progression (or death) will be censored at the last visit where the patient is documented to be progression free. Patients without disease assessment post-baseline will be censored at the randomization date. As needed, we will use Table 3 to specify how dates of progression events and dates for censoring of progression data are assigned. Table 3 represents an analysis that only includes well-documented and verifiable progression events. In Table 3, the progression dates are:

- Based only on radiological assessments verified by an IRC and symptomatic deterioration date assessed by study investigator.
- Assigned to the first time when tumor progression was noted.
- The date of death when the patient is closely followed. However, deaths occurring after two or more missed tumor assessments (> 91 days after last tumor assessment) are censored at the last visit.

Progressive disease will be assessed by the unidimensional measurements approach of the Immune-related Response Criteria.

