Death before first PD assessmentDate of deathProgressedDeath between adequate assessment visitsDate of deathProgressedDeath or progression after two or more missed visitDate of last tumor assessmentCensoredNew anti-cancer therapy or radiotherapy or surgery at a lesion siteDate of last tumor assessment where the patient was documented as progression free prior to the interventionCensored	more missed visit		
Death between adequate assessment visitsDate of deathProgressedDeath or progression after two or more missed visitDate of last tumor assessmentCensoredNew anti-cancer therapy or radiotherapy or surgery at a lesion siteDate of last tumor assessment where the patient was documented as progression free prior to the interventionCensored	Death before first PD assessment	Date of death	Progressed
visits       Death or progression after two or more missed visit       Date of last tumor assessment       Censored         New anti-cancer therapy or radiotherapy or surgery at a lesion site       Date of last tumor assessment where the patient was documented as progression free prior to the intervention       Censored	Death between adequate assessment	Date of death	Progressed
Death or progression after two or more missed visitDate of last tumor assessmentCensoredNew anti-cancer therapy or radiotherapy or surgery at a lesion siteDate of last tumor assessment where the patient was documented as progression free prior to the interventionCensored	visits		
missed visit     Date of last tumor assessment where the patient was     Censored       New anti-cancer therapy or radiotherapy or surgery at a lesion site     Date of last tumor assessment where the patient was     Censored	Death or progression after two or more	Date of last tumor assessment	Censored
New anti-cancer therapy or radiotherapy or surgery at a lesion siteDate of last tumor assessment where the patient was documented as progression free prior to the interventionCensored	missed visit		
radiotherapy or surgery at a lesion site   documented as progression free prior to the intervention	New anti-cancer therapy or	Date of last tumor assessment where the patient was	Censored
	radiotherapy or surgery at a lesion site	documented as progression free prior to the intervention	
prior to confirmed progression (or	prior to confirmed progression (or		
death)	death)		
No progression or Death         Date of last tumor assessment         Censored	No progression or Death	Date of last tumor assessment	Censored

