# 5.1.2.4 Distant Metastasis-Free Survival (DMFS)

Distant metastasis free survival (DMFS) in months is calculated as (first metastasis new lesion scan date or death date within 2 missed scheduled tumor assessment – date of randomization + 1)/30.4375. Patients without metastasis and death are censored at the date of the last disease assessment. Patients without post-baseline disease assessment are censored at randomization date.

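### The SAP censors patients with no post-baseline scan at randomization without exempting deaths, contradicting Table 3 for PFS and the event definitions for DMFS and time to new lesion (Definition 2)

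*SAP*

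**What the plan says.** The Protocol (10.2.2.4.1) defines PFS as the "time from randomization to disease progression or death (any cause), whichever occurs first". It has no rule that censors unscanned patients at randomization. SAP section 8 says the SAP prevails where the two differ.

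SAP 5.1.1.1 also ends PFS at progression or death from any reason. Among its censoring rules it adds: "Patients without disease assessment post-baseline will be censored at the randomization date". It then introduces Table 3: "As needed, we will use Table 3 to specify how dates of progression events and dates for censoring of progression data are assigned". Table 3 has a row for "Death before first PD assessment", dated at death with outcome progressed. It uses the randomization date only for patients with no baseline tumor assessment. Deaths after two or more missed assessments (more than 91 days after the last one) are censored.

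SAP 5.1.2.4 counts death within two missed scheduled assessments as a DMFS event, then says: "Patients without post-baseline disease assessment are censored at randomization date". SAP 5.1.3.4, Definition 2 of time to new lesion, has the same structure. Neither has a table.

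SAP 5.1.2.1 estimates the 6-month PFR by Kaplan-Meier. SAP 7.6.2.1 treats an 80% lower confidence limit above 25% as a signal.

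**The concern.** The first on-treatment scan is at Week 6. A patient who dies before it has no post-baseline assessment. Under the sentence in the text that patient is censored at time zero; under Table 3 the patient has an event at the date of death. Two programmers could code the same death in these two ways, and each could cite SAP 5.1.1.1.

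The choice matters because this censoring is informative. The patients removed are those with the worst outcome, so the remaining risk set looks better than the randomized arm. PFS is a primary endpoint, and its censoring carries into the 6-month PFR and that endpoint's signal rule. DMFS is exposed in the same way.

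**Working it through.** **1. The plan's own figures.** Inputs are from Protocol 10.3 and 10.3.1 and SAP 4: medians of 3 and 5.2 months with exponential survival, 40 patients per arm, alpha 0.10, beta 0.15, at least 6 of 18 progression free at stage 1 and at least 14 of 40 at the end.

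- 6-month PFR = 2^(−6/median): 2^(−6/3) = 25.0% and 2^(−6/5.2) = 44.9%, as stated.
- Exact two-stage error, summing over x ≥ 6 of 18 the product P(X1 = x) × P(X2 ≥ 14 − x of 22): alpha 0.080 at 25%, power 0.856 at 45%. Both meet the stated limits.
- With stage 1 non-binding: P(X ≥ 14 of 40) = 0.103 at 25% and 0.925 at 45%.

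**2. Count needed for the SAP signal.** Assume every patient is followed to 6 months with no other censoring. Then S = x/n, and Greenwood's variance with a log-log transform gives

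lower 80% limit = S^exp(1.2816 × √((1−S)/(nS)) / |ln S|).

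If k unscanned deaths are censored at randomization, n = 40 − k.

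| k censored at time zero | n | Smallest x that signals | Its lower limit | Lower limit for x − 1 |
|---|---|---|---|---|
| 0 | 40 | 14 | 25.5% | 23.3% |
| 1 | 39 | 14 | 26.2% | 23.9% |
| 2 | 38 | 14 | 26.9% | 24.6% |
| 3 | 37 | 13 | 25.3% | 22.9% |
| 4 | 36 | 13 | 26.0% | 23.5% |
| 5 | 35 | 13 | 26.8% | 24.3% |

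The SAP does not name the interval's transform. The linear form gives the same counts for k = 0 to 5. With early deaths counted as events (k = 0), the signal needs 14 of 40, which matches the Protocol's count. With one or two such deaths the required count stays at 14, but the estimate still rises: 10 progression-free patients are 10/40 = 25.0%, 10/39 = 25.6% or 10/38 = 26.3%.

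**3. Chance of a false signal.** Let d be the probability that a patient dies unscanned and is censored at time zero. The documents do not give d, so a range is assumed. With the true PFR among all randomized patients held at 25%, the rate among those remaining is 0.25/(1 − d). The probability is the sum over k of P(K = k of 40; d) × P(X ≥ required count of 40 − k; 0.25/(1 − d)).

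| Assumed d | False-signal probability |
|---|---|
| 0% | 10.3% |
| 2.5% | 10.8% |
| 5% | 12.5% |
| 7.5% | 14.8% |
| 10% | 17.5% |

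Conditional on exactly three such deaths, the remaining rate is 10/37. Then P(X ≥ 13 of 37) = 0.176, against P(X ≥ 14 of 37) = 0.100 if the required count had stayed at 14.

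**The case against.** For PFS, Table 3 names this exact case and counts it as an event. A case left unclear by the text is arguably one where the table is needed. The Efficacy set (SAP 6.3) also keeps patients who died before two missed assessments. In 5.1.2.4 the sentence directly follows the rule for patients without metastasis and death, so it can be read as supplying a date only for event-free patients. Definition 2 can be read the same way. All of this shows what was probably intended. It does not settle precedence for PFS, and for DMFS and Definition 2 the benign reading rests on the order of sentences alone.

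The size is also open to challenge. Three deaths in 40 is 7.5%, while eligibility (ECOG 0 or 1, capped tumor burden) points to few early deaths. At assumed rates of 1% and 2% the false-signal probability is 10.4% and 10.6%, close to the 10.3% base. That stands: at low rates the effect is small.

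A reader might infer that the SAP plans to delete early deaths from PFS and so lowers the bar for going forward. The documents do not support that. Table 3 says the opposite, the 25% threshold does not move, SAP 7.6.2.1 describes only a signal, and the interim futility rule is non-binding.

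**Conclusion.** The point holds as an unresolved contradiction. For PFS it lies between text and table, with no stated precedence. For DMFS and Definition 2 it lies between the censoring sentence and the event definition, with nothing to resolve it, so the wording is weaker there. Neither of those two endpoints feeds the PFR signal.

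If the sentence is followed literally, PFS, the 6-month PFR and DMFS are biased upward. For the PFR the false-signal probability goes from 10.3% to between 10.8% and 17.5% for assumed early-death rates of 2.5% to 10%. The required count drops from 14 to 13 only with three or more unscanned deaths in one arm. These figures assume no other censoring before 6 months. Unscanned patients who die after two missed assessments are censored under either reading. OS does not change, nor does the Protocol's 14 of 40 if it is applied as a plain count.

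**What to change.** In SAP 5.1.1.1, state that Table 3 governs which outcomes are PFS events, and replace the sentence with: *Patients with no post-baseline disease assessment and no PFS event under Table 3 (including death or symptomatic deterioration before the second missed assessment) are censored at randomization.* Symptomatic deterioration has to be named because Table 3 counts it as progression before the first assessment. A sentence limited to living patients would still censor those cases at time zero.

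In 5.1.2.4 and in Definition 2 of 5.1.3.4, use: *Patients with no post-baseline assessment and no death within 2 missed scheduled assessments are censored at randomization.* Earlier deaths are then events at the date of death, and unscanned patients who die later are censored at randomization. Definition 1 of time to new lesion excludes death by design and needs no change.

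The cost is one sentence in each of three places plus a statement of precedence, made before database lock. No new data are needed.

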5.7 Overall Study Duration and Follow-Up

The expected duration of patient participation on study treatment is 2.1 years. The study period will consist of Screening (study Day -30 to -1), Treatment Phase (study Days 0 to 84), Booster Phase (in the combined treatment arm) with continuation of G305 boosters (post Day 84 to 1 year [post Day 0] or until disease progression), Maintenance Phase with continuation of atezolizumab treatment (for the combined treatment arm, 1 year to 2 years [post Day 0] and, for the control arm, post Day 84 to 2 years [post Day 0], or until disease progression), and Survival Follow-up Phase (quarterly thereafter). The overall study duration will depend on speed of enrollment and time to the number of events.

Following completion of CMB305 dosing, patients will continue with imaging and clinical assessment every 6-9 weeks until disease progression, as defined by the RECIST v1.1 criteria modified to use irRC ([Section 6.3](#)). Patients or their physicians will then be contacted by the sites every 3 months by telephone to assess OS.

For patients receiving CMB305, blood will be collected to test for LV305 persistence at baseline and then at 6, 12, and 24 months following the first study treatment administration. Depending on the results from the 12-month sample, annual assessments may continue until 2 consecutive yearly samples show no evidence of LV305 persistence.

Patients with confirmed radiographic disease progression by irRC will be followed thereafter by the site every 3 months by contacting their primary physician by telephone as long as they are able to engage in follow-up until date of death recorded. Follow-up telephone contact will ascertain vital status, as well as possible occurrence of second malignancies and any SAE that might be possibly related to CMB305 treatment.

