#### IMDZ-C232

Peripheral blood will be collected for immunogenicity assays at baseline, then on Days 42, 70, and 98 ( $\pm$  2weeks). Tissue biopsies will be taken in each treatment group from consenting subjects before treatment and on Day 42, on Day 98 ( $\pm$  2 weeks), at 6 months or longer (for patients with treatment response), and at the time of progression to assess immune cell invasion, including changes in PD-L1, CD4, CD8/Ki-67 and/or CD3/perforin expression. If a patient undergoes a tumor biopsy at any time after disease progression, investigators are strongly encouraged to provide biopsy tissue to the sponsor for immune response and tumor changes analysis.

Imaging will be performed approximately every 6 weeks for 12 months, then every 12 weeks for tumor staging until progression. Tumor responses will be assessed at the sites by evaluating tumor images/scans using RECIST (v1.1) modified to use irRC-specified confirmation and unidimensional tumor measurements. Adjudication will be performed by blinded independent central review (BICR) following the same rules. The irRC modification requires a confirmation of CR/PR/progressive disease (PD) at least 4 weeks later with imaging; once confirmed, the date of progression is defined as the first date that the total tumor burden was shown to have increased by at least 20% compared with the nadir.

Patients will be followed until confirmed radiographic disease progression to determine ORR and PFS. In addition, OS status will be followed up until the end of the trial. If a patient dies, the date of death will be documented by the local physician and/or registries.

All SAEs, DLTs, and medical events of interest (MEOIs) deemed potentially related to the study agents will be reviewed by the Sponsor and an independent Data Monitoring Committee (DMC).

Following completion of CMB305 dosing, patients will continue with clinical assessment and imaging approximately every 6 weeks until disease progression, as defined by RECIST (v1.1) modified to use irRC. The expected duration of a patient's participation in the trial is up to 2.1 years, including Screening, Treatment Phase, Booster Phase (for patients in the combined treatment arm), and Maintenance Phase (with follow-up visits until disease progression). Patients will then enter the Survival Follow-up Phase and their physicians will be contacted every 3 months by telephone to assess OS.

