#### IMDZ-C232

Abbreviations: AE = adverse event, CT = computed tomography; ECG = electrocardiogram; ECOG = Eastern Cooperative Oncology Group; HepB = hepatitis B; HepC = hepatitis C; HIPAA = Human insurance Portability and Accountability Act; HIV = Human immunodeficiency Virus; meds = medications; mos = months; PBMC = peripheral blood mononuclear cells; SAE = serious adverse event.

- a. A window of ±3 days is permitted for Visits 3 through 12. Follow-up phase visits (Visits 13+) will be permitted a window of ±4 days, Tumor assessments will be permitted a window of ±1 week.
- b. Patients will be followed with visits every 3 weeks (±4 days) for 2 years (from Day 0) for until progression. Tumor size will be assessed every 6 weeks for the first year, then every 12 weeks until progression. Patients will then have no further staging procedures. Tumor biopsies will be obtained at 6 months or longer for patients with treatment response. Tumor biopsies will also be obtained at time of progression.
- c. Informed consent and HIPAA authorization must be signed before any screening study-related procedures are initiated. Three informed consents will be used: one to screen tumor sample for NY-ESO-1, one to engage in the study protocol, and an agreement to continue in the study and obtain peripheral blood samples and biopsies if the patient meets the criteria for progressive disease but wishes to remain on study.
- d. Documentation of NY-ESO-1 expression in prior tumor samples may have been collected from any procedure performed before baseline activities. There is no time limit for use of the results from the IMDZ-approved central lab.
- e. Vital sign measurements include temperature, pulse, respiratory rate, and resting systolic and diastolic blood pressure. On the day of each dosing, vital signs will be obtained pre-dosing and 30 minutes after dosing. For the first atezolizumab infusion, the patient's vital signs (HR, respiratory rate, BP, and temperature) should be measured within 15 minutes of the infusion, during the 60-minute infusion (every 15 [± 5] minutes), and 30 minutes after the infusion. For subsequent infusions, vital signs do not need to be obtained during the infusion if the prior infusion was tolerated without symptoms.
- f. Once the baseline physical exam has been conducted, a simple symptom-directed physical exam should be performed for all subsequent visits. Height and weight will be collected at Day 0 only.

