- g. Imaging will be performed by CT scan as defined by RECIST/irRC at screening and every 6 weeks after first study injection for the first year, then every 12 weeks for tumor staging until disease progression and includes a confirmatory scan performed at least 4 weeks later. Magnetic Resonance Imaging (MRI), bone scans, or PET/CT at baseline or subsequent visits will be performed only if clinically indicated.
- h. An HIV screening test will be repeated on Day 168 to determine if seroconversion has occurred following LV305 injections. If positive, further testing can demonstrate that the normal complement of HIV proteins is not present (unless the patient has developed a true HIV infection).
- i. Blood for immunogenicity will be collected at clinical sites that are trained in peripheral blood mononuclear cells (PBMC) isolation. Baseline samples will be drawn twice to ensure a good yield. At least 55 mL should be collected in 8 Cell Preparation Tubes (CPT)TM tubes for T-cell response assays. See the Lab Manual for processing details.
- j. Initial safety labs are to be performed within 4 days before treatment initiation. On treatment days during the study dosing period, the hematology and clinical chemistry laboratories must also be performed and reviewed before dosing and may be performed up to 48 hours prior to the planned dosing.
- k. Thyroid function tests (triiodothyronine [T3], thyroxine [T4], and thyroid stimulating hormone [TSH]) should be taken at initial screening and at least every 3 months while being treated with atezolizumab. As thyroid disorders could occur at any time as a result of atezolizumab treatment, patients should be monitored for changes in thyroid function for clinical signs and symptoms of thyroid disorders (at the start of treatment, periodically during treatment, and as indicated based on clinical evaluation).
- Urine pregnancy test must be performed for women of childbearing potential within 72 hours before study drug administration and negative before study drug administration, including during the follow-up period if patients are still receiving booster doses of G305 and/or atezolizumab. Serum pregnancy test may be performed if the site's standard operating procedures allow.
- m. Booster doses of G305 will be given 6 weeks following the Day 84 dose and every 6 weeks thereafter for 1 year (from Day 0) or until disease progression at the staging visits.

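### The SAP's 91-day gloss on two missed tumor assessments fits only 6-weekly scans; on the 12-weekly schedule it is one missed scan, so a late death can be coded as a PFS event or as censored

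*SAP*

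**What the plan says.** SAP 5.1.1.1 states the missed-assessment rule three times.

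- Main paragraph, by count only: "Patients with two or more missing response assessments prior to a visit with progression (or death) will be censored at the last visit". Protocol 10.2.2.4.1 has the same rule.
- Table 3, by count only: "Death or progression after two or more missed visit" leads to censoring at the last tumor assessment.
- Bullet on deaths introducing Table 3, by count with a day figure attached: "deaths occurring after two or more missed tumor assessments (> 91 days after last tumor assessment) are censored at the last visit".

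The scan interval is not constant. SAP 3.1 says "Imaging will be performed approximately every 6 weeks for 12 months, then every 12 weeks for tumor staging until progression", and note g to SAP Table 1 agrees: "every 6 weeks after first study injection for the first year, then every 12 weeks for tumor staging until disease progression". Note a adds "Tumor assessments will be permitted a window of ±1 week". Neither document gives a second day limit for the 12-weekly period.

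**The concern.** A count of missed scans and a fixed number of days are equivalent only if the interval is fixed, and here it doubles after the first year. A programmer who counts scheduled scans and one who takes a date difference and compares it with 91 will agree in year 1. They will disagree on some later deaths. PFS is a primary endpoint of an open-label trial, so its censoring rule should have one reading before the data are analyzed. The protocol's count does not settle the matter by itself, because SAP section 8 gives the SAP precedence and both readings are in the SAP. Table 3 adds a smaller uncertainty: it counts visits, and clinic visits are 3-weekly, while the other two statements count tumor assessments.

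**Working it through.** **Inputs.** Interval 42 days in year 1, then 84 days (SAP 3.1; SAP Table 1 note g). Window ±7 days (note a). Planning median PFS 3 and 5.2 months, exponential, 40 per arm (SAP section 4).

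**Limits.** Days until the window of the k-th missed scan closes = sum of the k intervals + 7.

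| Schedule after the last scan | One missed | Two missed |
|---|---|---|
| both 6-weekly | 42 + 7 = 49 | 2 × 42 + 7 = **91** |
| across the switch | 42 + 7 = 49 | 42 + 84 + 7 = 133 |
| both 12-weekly | 84 + 7 = **91** | 2 × 84 + 7 = 175 |

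The plan's figure is reproduced exactly in the first row. In the last row the same 91 days means one missed scan. The middle row assumes that the first 12-weekly scan falls 12 weeks after the last 6-weekly one; the documents do not fix that date.

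**Deaths in dispute.** On 12-weekly scans the second scan is not due until day 168 after the last one, and its window closes on day 175. A death on days 92–167 has at most one missed scan, so the count makes it an event and the day figure censors it. Days 168–175 depend on whether a scan counts as missed when due or when its window closes.

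**When it starts.** If 6-weekly scans end at Week 48, the earliest affected last scan is nominally Week 42 (Day 294). The earliest affected death is then at about Day 294 + 92 = 386, or 386/30.4375 = 12.7 months.

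**Who is exposed.** Progression-free at 12 months: 40 × 0.5^(12/3) = 2.5 and 40 × 0.5^(12/5.2) = 8.1 per arm.

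**How many deaths change status.** This was simulated with 400,000 patients per scenario. The documents give no rates, so the following are assumptions: 5–30% of scans missed, 10–25% of the PFS hazard being death without progression, median 12 months from progression to death, and scan dates uniform within ±7 days. A scan counted as missed if it was not performed and its window had closed before death.

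| Follow-up | Median 3 months | Median 5.2 months |
|---|---|---|
| 30 months, deaths per 40 | 0.03–0.24 | 0.09–0.62 |

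With 36 months of follow-up the maximum is 0.67. The chance that an arm of 40 has at least one such death is 3–48%.

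**Effect on planned estimates.** The mean shift in Kaplan-Meier PFS (day rule minus count rule) is 0.000 at 6 months and −0.0013 to 0 at 12 months. The small negative value arises because censoring back at the last scan removes the patient from the risk set earlier. Under the exponential, the 75/50/25% points fall at 1.25/3/6 months for a median of 3 months (for example, 2 × 3 = 6) and at 2.2/5.2/10.4 months for a median of 5.2 months, all before month 12.

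**The case against.** The strongest reply is that the count already governs. It is the operative wording in all three SAP statements and in the protocol. The day figure is a gloss in one bullet, attached to a table used as needed, and SAP section 1 says that dataset specifications will detail the programming rules. This largely stands: the problem is loose wording with an incorrect equivalence, and the main PFS definition is not itself in conflict. It does not remove the point, because 91 is the only day figure in the rule and is the easier version to program.

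Second, no planned PFS figure moves materially. The planned landmarks are 3, 6 and 12 months; 18 and 24 months are planned for OS only. This stands, with one qualification. At the 5.2-month median, the upper confidence limit of the 25% survival time, which the protocol's primary analysis reports, lies beyond 12 months in about 84% of simulated arms of 40. That limit can fall in the affected part of the curve.

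Third, the simulated range depends on its assumptions. It leaves out symptomatic deterioration as an event and censoring at new therapy, both of which would take deaths out of the disputed zone. This stands; the upper end is a corner case.

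Fourth, a fixed day limit could be a deliberate choice, since the bullet is concerned with closely followed patients. That would be defensible, but it would be a different rule and should not be presented as equivalent to two missed scans.

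A reader might also infer from the imaging sentences that patients will be scanned 9-weekly and that the 6-month rate is at risk. SAP 3.1 also says "patients will continue with clinical assessment and imaging approximately every 6 weeks until disease progression", and Protocol 5.7 says "patients will continue with imaging and clinical assessment every 6-9 weeks until disease progression" (Protocol 9.3.1 is similar). These sentences do disagree with the schedules of events. However, Protocol 9.1 refers to those schedules for timing, and Protocol 8.2.3 repeats 6-weekly scans for the first year. The documents therefore do not support a numerical consequence.

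**Conclusion.** The day figure is wrong as a stand-in for two missed scans once scans are 12-weekly, and a few late deaths could be coded either way. That much is exact arithmetic. The size is small: well under one death per arm of 40 on average, under the stated assumptions and planning medians. It is confined to PFS after about month 12, meaning the tail of the Kaplan-Meier plot and the exploratory hazard ratio. If true PFS is longer than planned, more patients reach the 12-weekly phase and the exposure grows.

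A reader might infer that the primary PFS result, or the 6-month futility assessment, is biased. The documents do not support that: the disputed deaths come too late to touch the 6-month rate, the point estimates of the quartiles lie before month 12 at the planning medians, OS does not use the rule, and comparisons between arms are exploratory. Nor is the direction always favorable, as the 12-month shift shows. The day figure is written for deaths only; for progression the SAP gives the count alone.

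**What to change.** Edit the SAP before database lock.

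- Delete the parenthesis with the 91-day figure. Define the rule as two or more consecutive scheduled tumor assessments not performed under the schedule in force, including the switch to 12-weekly scans. State that a late but completed scan is not missed, and whether a scan becomes missed on its due date or when its window closes.
- Use the same words in Table 3 in place of missed visits.
- State the date of the first 12-weekly scan.
- Alternatively, keep a day limit that depends on the schedule: about 91, 133 or 175 days for the three rows of the table above. Label it approximate, because the last scan may itself be up to a week early or late.

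The same definition can serve the DMFS, time-to-new-lesion and Efficacy set rules, which also refer to two missed assessments.

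The cost is one deleted parenthesis, one programming rule and a few words in Table 3, with no added scans or patients.

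As a separate minor consistency note, the imaging-interval sentences in Protocol 5.1, 5.7 and 9.3.1 and SAP 3.1 should be reconciled with the schedules of events. The protocol sentences would need an amendment under Protocol 16.1, so they could wait for the next one; the PFS fix does not depend on it.
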